5.3 Initial dose and schedule

Advanced EGFR mutant NSCLC and EGFR-TKI naïve patients, will be randomized to:

- Arm A: osimertinib 80 mg QD until RECIST 1.1 progression.
- Arm B: gefitinib 250mg QD until cfDNA T790M positive test (criteria for defining progression disease), irrespective of RECIST 1.1 criteria, then patients will receive osimertinib 80 mg QD until RECIST 1.1 progression. If patients have RECIST 1.1 progression without cfDNA T790M positive test, they will be switched to osimertinib.
- Arm C: gefitinib 250mg QD until RECIST 1.1 progression, irrespective of cfDNA T790M test, then patients will receive osimertinib 80 mg QD until RECIST 1.1 progression.

Continuation of osimertinib post-PD is allowed on individual basis provided that in the opinion of treating physician, patient may benefit from this therapy (please refer also to section 4.1).

Osimertinib or gefitinib must be swallowed with a glass of water and must not be mashed or chewed. The tablets can be taken preferably in the morning with or without meals

The initial dose of osimertinib 80 mg once daily can be reduced to 40 mg once daily. The initial dose for gefitinib (250 mg once daily) cannot be reduced to a lower dose.

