5.7.4 Other concomitant therapies

In case of RECIST 1.1 progression on a known lesion during osimertinib treatment, surgery, radiotherapy and cryotherapy will be allowed.

No other systemic anticancer therapies will be allowed.

Administration of Covid vaccine will be a treating physician decision after evaluation of benefit-risk ratio and depending of local vaccine availability and compliance with local regulatory guidelines. In cancer patients, the use of inactivated virus vaccines are usually permitted and live vaccines are generally prohibited in those receiving immunosuppressive treatments. Information on the mRNA based COVID-19 vaccines when used in cancer patients is currently not available. See Appendix F for EMA recommendations.

6 Clinical evaluation, laboratory tests and follow-up

As described in chapter 4, a cycle of treatment is defined as 28 days of once daily treatment with osimertinib or gefitinib.

In arm A, after 24 weeks, the duration between study visits will change from every 28 days (4 weeks) to every 56 days (8 weeks).

In arm B and C, study visits will be every 28 days (4 weeks) until the switch to osimertinib. After that, one visit will be performed 28 days after osimertinib initiation, the second one at 8 weeks with radiological evaluation and then every 56 days (8 weeks) if no progression on the first CT scan after osimertinib initiation.

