7.3.5 Evaluability for safety

All patients who have started the treatment (either gefitinib or orsimertinib) will be included in overall safety analyses.

For hematological events, the medical review team may decide that blood counts have not been performed and/or reported according to the protocol and are therefore inadequate for the evaluation of one/several hematological parameters in some patients.

Parameters that will be identified and monitored will be the following:

- Any grade 3-4 non hematological or grade 4 hematological toxicity at least possibly related to the treatment;
- % of treatment interruptions, schedule modifications and dose modifications;
- Compliance to the requirement of minimum dose intensity of 70% (treatment tolerability rule);
- Unexpected grade 2 toxicity at least possibly related to the treatment;
- Worsening of toxicity if data will be available at the time of DSM.

Patients who have discontinued treatment because of toxicity will always be included in the safety analyses.

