8.2.5 Data recoding and display

Frequency tables will be tabulated (by treatment group or otherwise) for all categorical variables by the levels of the variables as they appear on the CRF (with %). Categories with a text field specification will be tabulated as categories and then supplemented by a listing with the following information for the patients fulfilling the condition for the specification (patient id, institution, treatment group, value of the item and text field contents).

Dates relating to events prior to entry will be presented as the delay in days (or weeks, months, or years) between the past event and the date of entry (date of randomization – date of past event + 1) and presented using the median and range. For example, on the randomization checklist, the date of last administration of prior treatment (or the date of first diagnosis of the cancer) will be presented as the time elapsed (in days, weeks, months or years, as appropriate) since the day of the last administration and the date of entry on study (date of randomization – last administration/diagnosis +1).

Other delays (e.g. re-treatment delays) are presented as continuous variables using the median and range.

Continuous variables for which a coding system exists (such as for laboratory data) will be recoded into categories (for adverse events, the grading scale specified in the protocol will be used). Whenever no specific scale exists, lab data will be categorized based on the normal range: for example, below the lower normal limit (when appropriate), within the normal range, above the upper normal limit (ULN) and the degree to which it is above the ULN (for example > 2.5 x ULN, > 5 x ULN, > 10 x ULN). For laboratory data, the nadir is generally displayed. The nadir in a given cycle is the lowest laboratory value in that cycle; the overall nadir for a patient is the lowest laboratory value among all cycles.

Other continuous variables (for example age, dose ...) are presented using the median and range (minimum, maximum).

DI observed =
$$\left[\frac{mg}{m^2 \times weeks}\right] = \frac{total \ dose \ \left[\frac{mg}{m^2}\right]}{total \ duration \ \left[weeks\right]}$$

The relative dose intensity is calculated as the ratio of the dose intensity as calculated above to the dose intensity indicated in the protocol. The dose intensity indicated in the protocol is obtained as the dose specified per cycle (in mg/m^2).

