The dose intensity and the relative dose intensity are presented using median and ranges. The relative dose intensity can also be presented in categories (≤70%, >70-90%, >90-110%, >110-120%.

If appropriate, continuous data may also be presented in categories (for example, age may also be grouped in decades).

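### Section 8.2.5 has two unit errors in relative dose intensity: a weekly rate is divided by a per-cycle dose (25% at full compliance), and mg/m² is used for flat-dose tablets

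*Combined protocol and SAP*

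**What the plan says.** Section 8.2.5 gives a formula for observed dose intensity: total dose in mg/m² divided by total duration in weeks. It continues: "The relative dose intensity is calculated as the ratio of the dose intensity as calculated above to the dose intensity indicated in the protocol". For the reference it says: "The dose intensity indicated in the protocol is obtained as the dose specified per cycle", with the unit given as mg/m². The sentence ends there, and nothing divides the per-cycle dose by the length of the cycle. On display it adds: "The relative dose intensity can also be presented in categories", with bands of ≤70%, >70-90%, >90-110% and >110-120%.

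The opening of chapter 6 fixes the cycle: "a cycle of treatment is defined as 28 days of once daily treatment with osimertinib or gefitinib". Section 5.3 gives the doses as flat daily amounts: "Arm A: osimertinib 80 mg QD until RECIST 1.1 progression" and "Arm C: gefitinib 250mg QD until RECIST 1.1 progression". Arms B and C use both drugs in sequence.

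Section 7.3.5, repeated in the protocol summary, lists among the safety parameters to be monitored: "Compliance to the requirement of minimum dose intensity of 70% (treatment tolerability rule". It does not say how dose intensity is to be calculated.

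**The concern.** There are two defects, and they are independent.

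1. **Time base.** The numerator is a rate per week and the reference is an amount per four-week cycle. Their ratio is too small by a factor of 4.
2. **Dose unit.** The formula is in mg/m², but no mg/m² dose exists in the protocol for either tablet. As worded, the reference value is undefined.

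A third point is a gap. One formula is given without naming a drug, and total duration is not defined in Section 8.2.5. The only treatment duration definition (Section 7.2.7) runs from randomization until osimertinib stops. If that were used in arms B and C, each drug's intensity would be diluted by time spent on the other.

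What is at stake is the 70% safety parameter. Section 8.2.5 contains the only definition of dose intensity in the documents, and its lowest display band is also cut at 70%. If the formula is applied as worded, tolerant and intolerant patients fall into the same band. If it is corrected without a written change, the unit, time base and handling of the two drugs are left to whoever runs the table, and may differ between safety monitoring and the final report.

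**Working it through.** The plan states no numerical relative dose intensity (RDI), so there is no figure to reproduce. The check applies the formula to the protocol's own doses.

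**Inputs**
- Cycle: 28 days = 4 weeks (opening of chapter 6).
- Osimertinib 80 mg daily: 80 × 7 = 560 mg per week; 80 × 28 = 2240 mg per cycle (Section 5.3).
- Gefitinib 250 mg daily: 250 × 7 = 1750 mg per week; 250 × 28 = 7000 mg per cycle (Section 5.3).
- Permitted reduced osimertinib dose: 40 mg daily, 280 mg per week (Section 5.3).

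**Formulas**
- Literal RDI = dose per week / protocol dose per cycle.
- Consistent RDI = dose per week / (protocol dose per cycle / 4 weeks).

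Both are worked in mg, because no mg/m² reference exists.

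| Patient | Literal RDI | Consistent RDI |
|---|---|---|
| Osimertinib 80 mg, every day | 560/2240 = 25% | 560/560 = 100% |
| Gefitinib 250 mg, every day | 1750/7000 = 25% | 1750/1750 = 100% |
| Osimertinib 80 mg on 70% of days (392 mg per week) | 392/2240 = 17.5% | 392/560 = 70% |
| Osimertinib 40 mg throughout | 280/2240 = 12.5% | 280/560 = 50% |

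To reach a literal 70%, a patient would need 0.70/0.25 = 2.8 times the planned dose. Everyone at or below the planned dose is therefore in the ≤70% band, and the three upper bands are empty.

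**Does mg/m² contribute to the 25%?** If both terms are divided by body surface area (BSA), it cancels: (560/BSA)/(2240/BSA) = 25% for any BSA. Only if the numerator alone were converted would the figure change. Over an assumed BSA of 1.5 to 2.1 m², which the documents do not give, it would be 560/1.5/2240 = 17% down to 560/2.1/2240 = 12%.

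**Does the end date of exposure matter?** Section 5.6.1 has osimertinib withheld for up to 3 weeks, and the patient withdrawn from study treatment if the toxicity has not resolved sufficiently. Take, as an illustration, one full-dose cycle (28 days), then 21 days withheld, then discontinuation. If exposure ends at the last dose taken, RDI = 28/28 = 100%. If it includes the final interruption, RDI = 28/(28 + 21) = 57%. The same patient falls on opposite sides of 70%.

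**The case against.** The strongest reply is that the intended meaning can be recovered. Section 8.2.5 has just defined dose intensity as a weekly rate and then calls the reference a dose intensity, and bands running to 120% make sense only if full compliance is about 100%. An analyst who saw 25% for every patient would stop and correct it. The mg/m² unit looks like template text, as does the reference to chemotherapy trials in Section 8.2.1. All of this stands, and it makes the matter a correction of wording. It does not make the written formula right.

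A reader might infer that compliant patients will be reported as failing the tolerability rule. The documents do not support that as a prediction. Section 7.3.5 does not cite Section 8.2.5, does not use the word relative, and attaches no action to the 70% figure. The link is an inference, though a strong one, because there is no other definition and both places use 70%.

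A reader might also infer that the mg/m² unit helps to produce the 25%. It does not, because it cancels when used in both terms.

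Finally, the formula appears without an introductory sentence, so some text may have been lost in reading the PDF. The sentence defining the reference is complete, so this lowers confidence only slightly.

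**Conclusion.** The point holds as two separate unit errors in Section 8.2.5. The time-base mismatch alone gives a literal RDI of 25% at full compliance for either drug, a quarter of the value clearly intended. The mg/m² unit leaves the reference undefined as written.

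The 25% rests on three assumptions: the 28-day cycle in chapter 6, the starting doses in Section 5.3, and the same dose unit in both terms. That the 70% parameter uses this formula is inferred.

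The consequence is limited. If computed literally, one monitored safety parameter would carry no information. It would be going too far to call this a threat to the trial's conclusions: the primary endpoint, the rule of 25 successes out of 49, the brain progression free survival comparison and the safety population do not use dose intensity. No interim analysis is planned, and no stopping or analysis decision is tied to the 70% figure.

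**What to change.** In Section 8.2.5:
- Replace mg/m² with mg.
- Define the protocol dose intensity as the protocol dose per cycle divided by 4 weeks, so that both terms are per week.
- Calculate the ratio separately for gefitinib and osimertinib, each over its own exposure period.
- State the end date of that period so that any final interruption before discontinuation is included.

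In Section 7.3.5 and the protocol summary, cross-refer the 70% parameter to this ratio.

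The cost is minor wording changes in the statistics, safety and summary sections of the protocol. No dose or clinical rule changes.

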8.3 Interim analyses

No interim analysis (IA) is foreseen in this protocol.

8.4 End of study

End of study occurs when all of the following criteria have been satisfied:

- 1. Thirty days after all patients have stopped protocol treatment
- 2. The trial is mature for the analysis of the primary endpoint as defined in the protocol
- 3. The database has been fully cleaned and frozen for this analysis

9 Trial Governance and Data Monitoring

9.1 Study committees

9.1.1 Study Management Group (SMG)

The Study Management Group is set up for this study. It consists of the EORTC Headquarters team in charge of running the study (clinical research physician, statistician, clinical scientist, project manager and data managers) and the principal study coordinator.

The EORTC Headquarter team is responsible for the day -to-day conduct of the trial. The Study Coordinator will assist the team in case of problems with patient evaluation (eligibility, treatment compliance, safety).

The Study Management Group also performs the medical review as indicated below.

9.1.2 Study Steering Committee (SSC)

The Study Steering Committee for this study is composed of the study coordinators, the representatives of Academic Groups collaborating to the study, at least one representative of the EORTC Headquarters (Study Clinical Research Physician or Clinical Scientist) and one representative of the EORTC.

This committee provides the general oversight of the study and has the executive power. The SSC monitors study progress and conduct and advises on its scientific credibility. The SSC will consider and act, as appropriate, upon the recommendations of the independent data monitoring committee.

9.1.3 Independent Data Monitoring Committee (IDMC)

The independent data monitoring committee for EORTC studies (IDMC) is in charge of the independent oversight of this study. The composition of the IDMC is described in EORTC Policy "Independent Data Monitoring Committees for EORTC studies" (ref. EORTC POL004) and its functioning is ruled by the charter annexed to the Policy.

The study-specific experts on the IDMC performing this review will be selected for their relevant expertise with the disease and/or treatments assessed in the study.

The IDMC reports its recommendations in writing to the Study Management Group through the project manager to the Study Steering Committee and other relevant parties (supporting bodies, collaborative groups...).

9.2 Data Monitoring

9.2.1 Monitoring during medical review meetings

The medical review will be performed on a regular basis by the medical representative assisted as needed by the study management group. The main study coordinator will, in particular, support the Study Medical Representative during the medical review process and will assist the team in case of problems with patient evaluation (safety, eligibility, treatment compliance). The main study coordinator is also responsible for the review and approval of the medical review plan and medical review reports.

If at any time during the course of the study, the medical review identifies safety signals or other elements that could affect the potential risks and benefits to the study participants. These will be reported to the Study Steering Committee and may trigger a review by the EORTC Independent Data Monitoring Committee (IDMC).

9.2.2 Monitoring by the IDMC

The IDMC will be asked to give advice on whether the accumulating data from the trial justifies continuing recruitment of further patients or further follow-up.

The IDMC will review the trial whenever safety problems or other elements are identified during the medical review or by the SMG and/or SSC that could affect the potential risks and benefits for study participants.

The IDMC will also review the intermediate reports of accumulating data according to the study interim monitoring plan described in the statistical section of this protocol. If a decision is made to continue without change, the IDMC may advise on the frequency of future reviews of the data on the basis of accrual and event rates.

While the trial is ongoing the accumulating data will generally remain confidential, unless the SSC and IDMC agree that the data should be made public.

10 Translational research

The translational research is not optional for this protocol. Any patient who consent to enter the trial will have to consent for the translational research.

10.1 Main objectives

The main objectives of translational research study are, but not limited to, the following:

- to describe quantitatively the presence of T790M EGFR mutations and original activating EGFR mutations in plasma of patients treated with gefitinib and osimertinib longitudinally within the arms and to compare the presence of these mutations across the arms A, B and C.
- to describe the associations between the presence of these mutations and response evaluations by RECIST 1.1 longitudinally within the arms.
- to describe the associations between the presence of these mutations and response and PFS to osimertinib in Arm A, B and C.
- to assess mechanisms of resistance to osimertinib in formalin-fixed paraffin-embedded (FFPE) samples obtained from patients at baseline and at the time of progression on osimertinib by next generation sequencing and compare the presence of molecular resistance alterations in tissue samples and plasma samples taken on progression.
- To assess pharmaco-kinetics and/or pharmaco-dynamics of the different drugs, as potential resistance mechanisms in blood samples taken at baseline and during the course of treatment.

Detailed statistical analysis plan will be presented in a separate document prior to TR analysis.

10.2 Human Biological material

- Blood sample that would have been taken during screening visit and treatment each visit (every 4 weeks) while patients are within active treatment with gefitinib or osimertinib. Note: if gefitinib or osimertinib is temporarily discontinued due to toxicity, plasma sample should still be obtained. The last plasma sample should be taken from patients who progress on osimertinib by RECIST 1.1 evaluation (all three arms). Please refer to chapter 6.
- FFPE processed biopsy samples at baseline (residual tumor from diagnostic sample) and from progressing tumor lesions obtained from patients receiving osimertinib.

10.3 Data storage, transfer and development of technical appendices

The translational projects will be the result of the work of collaborating institutions and EORTC HQ. Statistical analysis plan will be jointly developed for each project. These documents will be developed and approved before starting any analysis. They will specify the analytical and methodological details. Clinical and patient-reported outcome data will be stored in the EORTC clinical database and biological investigational data will be stored in respective collaborating institutions. Transfer of data will be performed according to applicable policies in each organization (e.g. EORTC POL008) or according to jointly approved data transfer charters.

10.4 General principles for human biological material (HBM) collection

Human biological material (HBM) collection involves the collection and storage of biological material, residual biological material or derivatives in compliance with ethical and technical requirements.

Biobanking refers to the chain of procedures that encompass the life cycle of the biological material, e.g. from collection, shipping to long term storage and use, and may also be subject to local regulation and/or national/international legislation.

In this study, biological material will be centralized and stored at Medical University of Gdansk. From here, the biological material will be used or distributed to the other research laboratories involved in the translational research (TR) projects specified in this protocol or defined in the future.

The following principles apply to storage of HBM:

- The biobank will have a designated manager responsible for collection and will act as a communication point with the EORTC.
- The collected HBM should be documented, i.e. the amount remaining and its location.
- The Study Steering Committee (SSC)/Group committee will be responsible for TR project review and prioritization, including the consideration of newly proposed TR projects not specified in the protocol. In the absence of a SSC, responsibilities of the SSC are transferred to the Group and/ or EORTC HQ as applicable.
- Final decisions on the use of HBM will be determined by a majority vote of the SSC/Group committee. Additional expertise may be sought through advisory non-SSC/Group committee members.

Access to HBM (see EORTC Biobanking Policy POL020): HBM may be used for another purpose for which it was originally collected, subject to meeting ethical principles/and is covered by informed consent/ethics approval. In the case of secondary use of HBM, (i.e. for new TR projects that are not specified in the clinical study protocol and that were not foreseen at the time of protocol writing) interested parties may apply for the use of HBM and will follow the next steps:

- A short description of the new TR projects will be written and submitted to EORTC HQ for coordination with the appropriate SSC/Group committee.
- The SSC/Group committee will prioritize the TR projects. Access procedures defined by the SSC/Group committee will build on the following key points:
 - Project prioritization
 - should be strongly based on scientific merit,
 - should consider the contribution of the different investigators to the trial and TR project,
 - will take into consideration if the applicant is an EORTC member or not (whilst maintaining the principle of access to the wider scientific community and commitments owed to study participants and ethical committees).

- Protection of confidentiality must be respected.
- An EORTC HQ feasibility check, including recommendations for regulatory and ethical matters and
 other restrictions on the use of the HBM, will take place. If in the event the HBM collections are still
 retained at individual clinical sites, the TR project leader and the involved EORTC Group are
 responsible for collecting and providing information on availability of HBM for the feasibility
 assessment.
- Prioritized TR projects will then be reviewed by the Translational Research Advisory Committee (TRAC).
- Once SSC/Group committee prioritization, the EORTC HQ feasibility assessment, and TRAC review are complete and when all applicable competent Ethics Committees approvals are in place and ethical principles are met, the TR project can be activated and HBM release and analysis can commence.
- The EORTC Board will mediate any disagreements of opinion between TRAC, the EORTC HQ feasibility assessment, the SSC/Group committee and the TR project leader(s), as needed.

11 Investigator authorization procedure

Investigators will be authorized to register and/or randomize patients in this trial only once they have returned the following documents to the EORTC Headquarters:

- The updated signed and dated curriculum vitae of the Principal Investigator in English (not older than 2 years) with a GCP training proof.
- The (updated) list of normal ranges for the investigator's institution signed and dated by the head of the laboratory. Please make sure normal ranges are provided also for those tests required by the protocol but not routinely done at the investigator's institution.
- The Confirmation of interest by Principal Investigator Form (CIF), stating that the investigator will fully
 comply with the protocol. This must include an estimate of yearly accrual and a statement on any
 conflict of interest that may arise due to trial participation.
- The Study Agreement between EORTC and investigator's institution.
- A copy of the favorable opinion of the local or national (whichever is applicable) ethics committee
 mentioning the documents that were reviewed (including the version numbers and version dates of
 all documents). A list of all members of the ethics committee is also requested.
- A copy of the translated and adapted (according to all national requirements) Patient Information /
 Informed Consent Sheet (PISIC). Version numbers and dates must be clearly stated on each page. The
 signature log-list of the staff members with a sample of each authorized signature and the indication
 of the level of delegations. In case patients receive treatment at a satellite institution, i.e. outside the
 authorized institution, details on the satellite institution, including the CV of the local investigator,
 normal lab ranges and the approval of an ethics committee will have to be transmitted to the EORTC
 Headquarters. Please keep in mind that all communication is done ONLY between the primary
 institution and the EORTC HQ.
- The full name, address, phone numbers and e-mail address of the local pharmacist who will be responsible for the trial medication (for any trial where the drug will be provided).
- An accreditation, a certification, an established quality control / external quality assessment or another validation should be provided for the own laboratory.

The center specific list of required documents will be included in the protocol activation package, with proper instructions as required by this protocol, your group and / or the applicable national law.

The new investigator will be added to the "authorization list", and will be allowed to register/randomize patients in the trial as soon as

- All the above-mentioned documents are available at the EORTC HQ.
- All applicable national legal and regulatory requirements are fulfilled.

Patient registration/randomization from centers not (yet) included on the authorization list will not be accepted.

12 Patient randomization procedure

Patient randomization will only be accepted from authorized investigators (see chapter on "investigator authorization procedure").

A patient can only be randomized after verification of eligibility. Both the eligibility check and randomization must be done before the start of the protocol treatment.

Subjects should be registered shortly after signing the informed consent the **EORTC online** randomization system (ORTA = online randomized trials access), accessible 24 hours a day, 7 days a week, through the internet. To access the interactive randomization program, the investigator needs a username and a password (which can be requested at http://orta.eortc.be/).

In case of problems EORTC participants can phone the EORTC Headquarters from 9.00 am to 5.00 pm (Belgian local time) from Monday through Friday to randomize patients via the EORTC call center. Randomization via the phone is not available on Belgian holidays. A list of these holidays is available on the EORTC web site (http://orta.eortc.be/) and it is updated annually.

Through Internet: http://orta.eortc.be/

In case of problems randomization by [contact]

